## 12.2 Disease Parameters

### 12.2.1 Measurable

12.2.1.1 Tumor lesions: Must be accurately measured in at least one dimension (longest diameter in the plane of measurement is to be recorded) with a minimum size of:

- 10mm by CT scan (CT scan slice thickness no greater than 5 mm).
- 10mm caliper measurement by clinical exam (lesions which cannot be accurately measured with calipers should be recorded as non-measurable).
- 20mm by chest X-ray.

12.2.1.2 Malignant lymph nodes: To be considered pathologically enlarged and measurable, a lymph node must be  $\geq 15$ mm in short axis when assessed by CT scan (CT scan slice thickness recommended to be no greater than 5 mm). At baseline and in follow-up, only the short axis will be measured and followed.

### 12.2.2 Non-measurable

All other lesions, including small lesions (longest diameter  $< 10$ mm or pathological lymph nodes with  $\geq 10$  to  $< 15$ mm short axis) as well as truly non-measurable lesions. Lesions considered truly non-measurable include: leptomeningeal disease, ascites, pleural or pericardial effusion, inflammatory breast disease, lymphangitic involvement of skin or lung, abdominal masses/abdominal organomegaly identified by physical exam that is not measurable by reproducible imaging techniques.

### 12.2.3 Special considerations regarding lesion measurability

Bone lesions, cystic lesions, and lesions previously treated with local therapy require particular comment:

#### 12.2.3.1 Bone lesions:

- Bone scan, PET scan or plain films are not considered adequate imaging techniques to measure bone lesions. However, these techniques can be used to confirm the presence or disappearance of bone lesions.
- Lytic bone lesions or mixed lytic-blastic lesions, with identifiable soft tissue components, that can be evaluated by cross-sectional imaging techniques such as

CT or MRI can be considered as measurable lesions if the soft tissue component meets the definition of measurability described above.

- Blastic bone lesions are non-measurable.

#### 12.2.3.2 Cystic lesions:

- Lesions that meet the criteria for radiographically defined simple cysts should not be considered as malignant lesions (neither measurable nor non-measurable) since they are, by definition, simple cysts.
- ‘Cystic lesions’ thought to represent cystic metastases can be considered as measurable lesions, if they meet the definition of measurability described above. However, if non cystic lesions are present in the same patient, these are preferred for selection as target lesions.

#### Lesions with prior local treatment:

- Tumor lesions situated in a previously irradiated area, or in an area subjected to other loco-regional therapy, are usually not considered measurable unless there has been demonstrated active tumor.
- Progression in the lesion. Study protocols should detail the conditions under which such lesions would be considered measurable.

### 12.2.4 Specifications by methods of measurements

#### 12.2.4.1 Measurement of lesions

All measurements should be recorded in metric notation, using calipers if clinically assessed. All baseline evaluations should be performed as close as possible to the treatment start and never more than 21 days before the beginning of the treatment.

#### 12.2.4.2 Method of assessment

The same method of assessment and the same technique should be used to characterise each identified and reported lesion at baseline and during follow-up. Imaging based evaluation should always be done rather than clinical examination unless the lesion(s) being followed cannot be imaged but are assessable by clinical exam.

**Clinical lesions:** Clinical lesions will only be considered measurable when they are superficial and  $\geq 10$ mm diameter as assessed using calipers (e.g., skin nodules). For the case of skin lesions, documentation by colour photography including a ruler to estimate the size of the lesion is suggested. When lesions can be evaluated by both clinical exam and imaging, imaging evaluation should be undertaken since it is more objective and may also be reviewed at the end of the study.

**Chest X-ray:** Chest CT is preferred over chest X-ray, particularly when progression is an important endpoint, since CT is more sensitive than X-ray, particularly in identifying new lesions. However, lesions on chest X-ray may be considered measurable if they are clearly defined and surrounded by aerated lung.

CT, MRI: CT is the best currently available and reproducible method to measure lesions selected for response assessment. Guidelines have defined measurability of lesions on CT scan based on the assumption that CT slice thickness is 5mm or less. When CT scans have slice thickness greater than 5 mm, the minimum size for a measurable lesion should be twice the slice thickness.

MRI is also acceptable in certain situations (e.g. for body scans).

Ultrasound: Ultrasound is not useful in assessment of lesion size and should not be used as a method of measurement. Ultrasound examinations cannot be reproduced in their entirety for independent review at a later date and, because they are operator dependent, it cannot be guaranteed that the same technique and measurements will be taken from one assessment to the next. If new lesions are identified by ultrasound in the course of the study, confirmation by CT or MRI is advised. If there is concern about radiation exposure at CT, MRI may be used instead of CT in selected instances.

PET/CT may not be used for RECIST or irRECIST measurements.

Endoscopy, laparoscopy: The utilisation of these techniques for objective tumor evaluation is not advised. However, they can be useful to confirm complete pathological response when biopsies are obtained or to determine relapse in trials where recurrence following complete response or surgical resection is an endpoint.

Tumor markers: tumor markers alone cannot be used to assess objective tumor response. If markers are initially above the upper normal limit, however, they must normalise for a patient to be considered in complete response.

Cytology, histology: These techniques can be used to differentiate between PR and CR in rare cases if required by protocol (for example, residual lesions in tumor types such as germ cell tumors, where known residual benign tumors can remain). When effusions are known to be a potential adverse effect of treatment (e.g. with certain taxane compounds or angiogenesis inhibitors), the cytological confirmation of the neoplastic origin of any effusion that appears or worsens during treatment can be considered if the measurable tumor has met criteria for response or stable disease in order to differentiate between response (or stable disease) and progressive disease.

## 12.3 Response Criteria

### 12.3.1 Target lesions

When more than one measurable lesion is present at baseline all lesions up to a maximum of five lesions total (and a maximum of two lesions per organ) representative of all involved organs should be identified as **target lesions** and will be recorded and measured at baseline (this means in instances where patients have only one or two organ sites involved a maximum of two and four lesions respectively will be recorded).

### 12.3.2 Evaluation of Target Lesions

12.3.2.1 Complete Response (CR): Disappearance of all target lesions. Any pathological lymph nodes (whether target or non-target) must have reduction in short axis to <10 mm.

12.3.2.2 Partial Response (PR): At least a 30% decrease in the sum of diameters of target lesions, taking as reference the baseline sum diameters.

12.3.2.3 Progressive Disease (PD): At least a 20% increase in the sum of diameters of target lesions, taking as reference the smallest sum on study (this includes the baseline sum if that is the smallest on study). In addition to the relative increase of 20%, the sum must also demonstrate an absolute increase of at least 5 mm. (Note: the appearance of one or more new lesions is also considered progression).

12.3.2.4 Stable Disease (SD): Neither sufficient shrinkage to qualify for PR nor sufficient increase to qualify for PD, taking as reference the smallest sum of diameters while on study.

#### 12.3.3 Non-target lesions:

All other lesions (or sites of disease) including pathological lymph nodes should be identified as **non-target lesions** and should also be recorded at baseline. Measurements are not required and these lesions should be followed as ‘present’, ‘absent’, or in rare cases ‘unequivocal progression’. In addition, it is possible to record multiple nontarget lesions involving the same organ as a single item on the case record form (e.g. ‘multiple enlarged pelvic lymph nodes’ or ‘multiple liver metastases’).

#### 12.3.4 Evaluation of Non-Target Lesions

12.3.4.1 Complete Response (CR): Disappearance of all non-target lesions and normalization of tumor marker level. All lymph nodes must be non-pathological in size (<10mm short axis).

#### 12.3.4.2 Non-CR/Non-PD:

Persistence of one or more non-target lesion(s) and/or maintenance of tumor marker level above the normal limits.

12.3.4.3 Progressive Disease (PD): Unequivocal progression of existing non-target lesions. (Note: the appearance of one or more new lesions is also considered progression).

#### 12.3.5 Evaluation of Best Overall Response

The best overall response is the best response recorded from the start of the study treatment until the end of treatment.

Table 3: Time point response

Target Lesions	Non-Target Lesions	New Lesions	Overall Response
CR	CR	No	CR
CR	Non CR/Non PD	No	PR

CR	Not evaluated	No	PR
PR	Non PD or not all evaluated	No	PR
SD	Non PD or not all evaluated	No	SD
Not all evaluated	Non PD	No	NE
PD	Any	Yes or no	PD
Any	PD	Yes or no	PD
Any	Any	Yes	PD

CR= completeresponse, PR= partial response, PD= progressive disease, SD= stable disease, NE= not evaluable.

\* In exceptional circumstances, unequivocal progression in non-target lesions may be accepted as disease progression.

Note: Patients with a global deterioration of health status requiring discontinuation of treatment without objective evidence of disease progression at that time should be reported as “*symptomatic deterioration*”. Every effort should be made to document the objective progression even after discontinuation of treatment.

## 12.4 Duration of Response

12.4.1 Duration of overall response: The duration of overall response is measured from the time measurement criteria are met for CR or PR (whichever is first recorded) until the first date that recurrent or progressive disease is objectively documented (taking as reference for progressive disease the smallest measurements recorded since the treatment started). The duration of overall CR is measured from the time measurement criteria are first met for CR until the first date that recurrent disease is objectively documented.

12.4.2 Duration of stable disease: Stable disease is measured from the start of the treatment until the criteria for progression are met, taking as reference the smallest measurements recorded since the treatment started.

## 12.5 Immune-Related Response Criteria

### 12.5.1 Introduction

Increasing clinical experience indicates that traditional response criteria (e.g., Response Evaluation Criteria in Solid Tumors, Version 1.1 [RECIST v1.1] and World Health Organization [WHO]) may not be sufficient to characterize fully activity in the new era of target therapies and/or biologics. In studies with cytokines, cancer vaccines, and monoclonal antibodies, complete response, partial response, or stable disease has been shown to occur after an increase in tumor burden as characterized by progressive disease by traditional response criteria. Therefore, conventional response criteria may not adequately assess the activity of immunotherapeutic agents because progressive disease (by initial radiographic evaluation) does not necessarily reflect therapeutic

failure. Long-term effect on the target disease must also be captured. The immune-related response criteria (irRC) are criteria that attempt to do that by enhancing characterization of new response patterns that have been observed with immunotherapeutic agents (i.e., ipilimumab). (Note: The irRC only index and measurable new lesions are taken into account.)

### 12.5.2 Glossary

Term	Definition
SPD	sum of the products of the two largest perpendicular diameters
Tumor burden	$SPD_{\text{index lesions}} + SPD_{\text{new, measurable lesions}}$
Nadir	minimally recorded tumor burden
irCR	immune-related complete response
irPD	immune-related progressive disease
irPR	immune-related partial response
irSD	immune-related stable disease
irBOR	immune-related best overall response

### 12.5.3 Baseline Assessment Using irRC

Step 1. Identify the index lesions (five lesions per organ, up to ten visceral lesions and five cutaneous lesions).

Step 2. Calculate the SPD of all of these index lesions:

$$SPD = \sum_i (\text{Largest diameter of lesion } i) \times (\text{Second largest diameter of lesion } i).$$

### 12.5.4 Post-baseline Assessments Using irRC

Step 1. Calculate the SPD of the index lesions.

Step 2. Identify new, measurable lesions ( $\geq 5 \times 5$  mm; up to five new lesions per organ: five new cutaneous lesions and ten visceral lesions).

Step 3. Calculate the SPD of the new, measurable lesions.

Step 4. Calculate the tumor burden:

$$\text{Tumor burden} = SPD_{\text{index lesions}} + SPD_{\text{new, measurable lesions}}$$

Step 5. Calculate the change in tumor burden relative to baseline and the change in tumor burden relative to nadir.

Step 6. Derive the overall response using the table below.

Overall Response	Criterion
irCR	Complete disappearance of all lesions (whether measurable or not, and no new lesions) confirmed by a repeat, consecutive assessment $\geq 4$ weeks from the date first documented

Overall Response	Criterion
irPR	Decrease in tumor burden $\geq 50\%$ relative to baseline confirmed by a consecutive assessment $\geq 4$ weeks from the date first documented
irSD	Criteria for irCR, irPR, and irPD are not met; does not require confirmation
irPD	Increase in tumor burden $\geq 25\%$ relative to nadir confirmed by a consecutive assessment $\geq 4$ weeks from the date first documented

irCR = immune-related complete response; irPD = immune-related progressive disease;  
 irPR = immune-related partial response; irSD = immune-related stable disease.

### 12.5.5 Determination of Immune-Related Best Overall Response (irBOR)

Once a patient has completed all tumor assessments, his/her irBOR may be determined:

Condition	irBOR
At least one irCR	irCR
At least one irPR and no irCR	irPR
At least one irSD and no irCR and no irPR	irSD
At least one irPD and no irCR, no irPR, and no irSD	irPD

irBOR = immune-related best overall response; irCR = immune-related complete response; irPD = immune-related progressive disease; irPR = immune-related partial response; irSD = immune-related stable disease.

## 12.6 Response Review and Central Tumor Measurements

At the end of treatment, all scans (baseline and through disease progression, along with crossover scans) should be sent on a CD to the address below for imaging correlatives. These do not need to be overnighted. Please include patient's study ID number the CD/disc.

### Address to send scans at the end of treatment

### **13. ASSESSMENT OF SAFETY ADVERSE EVENT REPORTING**

Safety assessments will consist of monitoring and reporting AEs and SAEs, all events of death, and any study-specific issue of concern.

#### **13.1 General**

Adverse event collection and reporting is a routine part of every clinical trial. This study will use the descriptions and grading scales found in the NCI Common Terminology Criteria for Adverse Events version 5.0 (CTCAE v.5.0) that is available at <http://ctep.cancer.gov/reporting//ctc.html>.

Information on all adverse events, whether reported by the participant, directly observed, or detected by physical examination, laboratory test or other means, will be collected, recorded, followed and reported as described in the following sections.

Adverse events experienced by participants will be collected and reported from initiation of study medication, throughout the study, and within 30 days of the last dose of study medication. Participants who experience an ongoing adverse event related to a study procedure and/or study medication beyond 30 days will continue to be contacted by a member of the study team until the event is resolved, stabilized, or determined to be irreversible by the participating investigator.

Participants should be instructed to report any serious post-study event(s) that might reasonably be related to participation in this study. The investigator should notify the IRB and any other applicable regulatory agency of any unanticipated death or adverse event occurring after a participant has discontinued or terminated study participation that may reasonably be related to the study.

#### **13.2 Risks Associated with atezolizumab**

The PD-L1/PD-1 pathway is involved in peripheral tolerance; therefore, such therapy may increase the risk of immune-related AEs, specifically the induction or enhancement of autoimmune conditions. AEs with potentially immune-related causes, including rash, hypothyroidism, hepatitis/transaminitis, colitis, myositis, and myasthenia gravis, have been observed in Study PCD4989g.

Although most immune-related AEs observed with immunomodulatory agents have been mild and self-limiting, such events should be recognized early and treated promptly to avoid potential major complications (Di Giacomo et al. 2010).

A more detailed safety profile of atezolizumab is provided in the atezolizumab Investigator's Brochure.

### 13.3 Safety Parameters and Definitions

#### 13.3.1 Adverse Event (AE)

An AE is any unfavorable and unintended sign, symptom, or disease temporally associated with the use of an investigational medicinal product (IMP) or other protocol-imposed intervention, regardless of attribution.

This includes the following:

- AEs not previously observed in the patient that emerge during the protocol-specified AE reporting period, including signs or symptoms that were not present prior to the AE reporting period
- Complications that occur as a result of protocol-mandated interventions (e.g., invasive procedures such as cardiac catheterizations)
- If applicable, AEs that occur prior to assignment of study treatment associated with medication washout, no treatment run-in, or other protocol-mandated intervention
- Pre-existing medical conditions (other than the condition being studied) judged by the investigator to have worsened in severity or frequency or changed in character during the protocol-specified AE reporting period
- Abnormal laboratory values or diagnostic test results constitute adverse events only if they induce clinical signs or symptoms or require treatment or further diagnostic tests.

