### 9.2.2 Hepatotoxicity

Immune-mediated hepatitis has been associated with the administration of atezolizumab.

While in this study, patients presenting with right upper-quadrant abdominal pain felt by the investigator to be possibly related to study treatment and/or unexplained nausea or vomiting should have LFTs performed immediately, and LFTs (AST/ALT) should be reviewed before administration of the next dose of study drug.

In the presence of LFT abnormalities, neoplastic, concurrent medications, viral hepatitis, and toxic etiologies should be considered and addressed, as appropriate. Imaging of the liver, gall bladder, and biliary tree should be performed to rule out neoplastic or other causes of increased LFTs. Anti-nuclear antibody, perinuclear anti-neutrophil cytoplasmic antibody, anti-liver kidney microsomal, and anti-smooth muscle antibody tests should be performed if an autoimmune etiology is suspected.

Patients with LFT abnormalities should be managed according to the guidelines in table below.

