#### Dose Modification Guidelines for Hepatic Events

Event	Management
Hepatic event, Grade 1	
CTCAE v4.0 guidelines
 
 
• Continue atezolizumab.
 
• Monitor LFTs until values resolve to within normal limits.
 

	
CTCAE v5.0 guidelines
 
 
• Continue atezolizumab.
 
• Monitor LFTs until values resolve to within normal limits or to baseline values.
 

Hepatic event, Grade 2	
All events:
 
 
• Monitor LFTs more frequently until return to baseline values.
 
 
Events of > 5 days' duration:
 
 
• Withhold atezolizumab for up to 12 weeks after event onset. aa
 
• Initiate treatment with corticosteroids equivalent to 1-2 mg/kg/day oral prednisone.
 
• If event resolves to Grade 1 or better, resume atezolizumab.b
 
• If event does not resolve to Grade 1 or better while withholding atezolizumab, permanently discontinue atezolizumab and contact Study Chair.c
 

Event	Management
Hepatic event, Grade 3 or 4	
 
• Permanently discontinue atezolizumab and contact Study Chair.c
 
• Consider patient referral to gastrointestinal specialist for evaluation and liver biopsy to establish etiology of hepatic injury.
 
• Initiate treatment with corticosteroids equivalent to 1-2 mg/kg/day oral prednisone.
 
• If event does not improve within 48 hours after initiating corticosteroids, consider adding an immunosuppressive agent.
 
• If event resolves to Grade 1 or better, taper corticosteroids over <math>\geq 1</math> month.
 

LFT = liver function tests. CTCAE = □ Common Terminology Criteria for Adverse Events

a Atezolizumab may be withheld for a longer period of time (i.e., > 12 weeks after event onset) to allow for corticosteroids (if initiated) to be reduced to the equivalent of  $\leq 10$  mg/day oral prednisone. The acceptable length of the extended period of time must be agreed upon by the investigator and the Study Chair.

b If corticosteroids have been initiated, they must be tapered over  $\geq 1$  month to the equivalent of  $\leq 10$  mg/day oral prednisone before atezolizumab can be resumed.

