**Management Guidelines for Endocrine Events (cont.)**

Event	Management
Symptomatic adrenal insufficiency, Grade 2-4	
 
• Withhold atezolizumab for up to 12 weeks after event onset. a
 
• Refer patient to endocrinologist.
 
• Perform appropriate imaging.
 
• Initiate treatment with corticosteroids equivalent to 1-2 mg/kg/day IV methylprednisolone and convert to 1-2 mg/kg/day oral prednisone or equivalent upon improvement.
 
• If event resolves to Grade 1 or better and patient is stable on replacement therapy, resume atezolizumab.b
 
• If event does not resolve to Grade 1 or better or patient is not stable on replacement therapy while withholding atezolizumab, permanently discontinue atezolizumab and contact Study Chair.c
 

Hyperglycemia, Grade 1 or 2	
 
• Continue atezolizumab.
 
• Investigate for diabetes. If patient has Type 1 diabetes, treat as a Grade 3 event. If patient does not have Type 1 diabetes, treat as per institutional guidelines.
 
• Monitor for glucose control.
 

Hyperglycemia, Grade 3 or 4	
 
• Withhold atezolizumab.
 
• Initiate treatment with insulin.
 
• Monitor for glucose control.
 
• Resume atezolizumab when symptoms resolve and glucose levels are stable.
 

Hypophysitis (pan-hypopituitarism), Grade 2 or 3	
 
• Withhold atezolizumab for up to 12 weeks after event onset. a
 
• Refer patient to endocrinologist.
 
• Perform brain MRI (pituitary protocol).
 
• Initiate treatment with corticosteroids equivalent to 1-2 mg/kg/day IV methylprednisolone and convert to 1-2 mg/kg/day oral prednisone or equivalent upon improvement.
 
• Initiate hormone replacement if clinically indicated.
 
• If event resolves to Grade 1 or better, resume atezolizumab.b
 

	
 
• If event does not resolve to Grade 1 or better while withholding atezolizumab, permanently discontinue atezolizumab and contact Study Chair. c
 
• For recurrent hypophysitis, treat as a Grade 4 event.
 

--	--

MRI=magnetic resonance imaging; TSH = thyroid-stimulating hormone.

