#### 9.3.1 Hematologic Toxicity

**At the start of each cycle if the patient is receiving carboplatin, the ANC must be  $\geq 1000/\text{mm}^3$  and the platelet count must be  $\geq 80,000/\text{mm}^3$ .** Platelets must be  $\geq 100,000$  for study entry. Growth factors may be used in accordance with American Society of Clinical Oncology (ASCO) and National Comprehensive Cancer Network (NCCN) guidelines (Smith et al. 2006; NCCN 2012). Upon recovery, dose adjustments at the start of a subsequent cycle will be made on the basis of the lowest platelet and neutrophil values from the previous cycle (see Table below).

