#### 9.3.2.1 Carboplatin Dose Modification on the Basis of Non-Hematologic

#### Toxicities in the Preceding Cycle

Toxicity	Adjusted Carboplatin Dose a
Diarrhea	Grade 3 or 4 b : 100% of dose
Oral mucositis	Grade 3 or 4: Decrease AUC by 1
Nausea/Vomiting	Grade 3 or 4: Decrease AUC by 1
Neurotoxicity (motor or sensory)	Grade 2: 100% of dose Grade 3 or 4: Decrease AUC by 1
Transaminase Elevation	Grade 3: Decrease AUC by 1 Grade 4: discontinue
Other	Grade 3 or 4: Decrease AUC by 1

AUC □ area under the concentration curve.

a If deemed appropriate by the treating physician, adjust carboplatin dose to the specified percentage of the previous AUC.

b Or any grade of diarrhea requiring hospitalization.

Nausea and/or vomiting should be controlled with adequate anti-emetics. If Grade 3 or 4 nausea/vomiting occurs in spite of anti-emetics, the dose should be reduced by 25% for the next course. If tolerated, the dose should be increased back to 100% as soon as possible.

If, on Day 1 of any treatment cycle, the patient has grade 2 oral mucositis, the treatment can be withheld until the oral mucositis is cleared. If the oral mucositis has not cleared in 3 weeks, the patient's chemotherapy will be discontinued. If acute Grade 3 oral mucositis occurs at any time, the dose should be given at a 75% dose when the oral mucositis is completely cleared. This is a permanent dose reduction.

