### 13.5.6 Assessment of Severity of Adverse Events

The adverse event severity grading scale for the NCI CTCAE (v5.0 Update current versions) will be used for assessing adverse event severity. Below Table should be used for assessing severity for adverse events that are not specifically listed in the NCI CTCAE.

Adverse Event Severity Grading Scale for Events Not Specifically Listed in NCI CTCAE

Grade	Severity
1	Mild; asymptomatic or mild symptoms; clinical or diagnostic observations only; or intervention not indicated
2	Moderate; minimal, local, or non-invasive intervention indicated; or limiting age-appropriate instrumental activities of daily living a

3	Severe or medically significant, but not immediately life-threatening; hospitalization or prolongation of hospitalization indicated; disabling; or limiting self-care activities of daily living b,c
4	Life-threatening consequences or urgent intervention indicated d
5	Death related to adverse event d

NCI CTCAE = National Cancer Institute Common Terminology Criteria for Adverse Events.

Note: Based on the most recent version of NCI CTCAE v.5.0 which can be found at:  
[http://ctep.cancer.gov/protocolDevelopment/electronic\\_applications/ctc.htm](http://ctep.cancer.gov/protocolDevelopment/electronic_applications/ctc.htm)

- a. Instrumental activities of daily living refer to preparing meals, shopping for groceries or clothes, using the telephone, managing money, etc.
- b. Examples of self-care activities of daily living include bathing, dressing and undressing, feeding oneself, using the toilet, and taking medications, as performed by patients who are not bedridden.
- c. If an event is assessed as a "significant medical event," it must be reported as a serious adverse event
- d. Grade 4 and 5 events must be reported as serious adverse events

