## 17.4 Statistical Analysis Plan

Demographic information, such as age and race, will be tabulated. Descriptive statistics, including means, standard deviations, and ranges for continuous parameters, as well as percents and frequencies for categorical parameters, will be presented. Investigation for outliers and assumptions for statistical analysis, e.g., normality and homoscedasticity, will be made. If necessary, data will be

transformed by utilizing appropriate transformations such as log or square root. Adverse medical events will be tabulated. NCI toxicity Grade 3 and Grade 4, and laboratory abnormalities will be listed.

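### Low-grade laboratory adverse events may be recorded more often on the combination because the steps that make them events are prescribed below Grade 3 only for atezolizumab, so their rates are not comparable between arms

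*Combined protocol and SAP*

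**What the plan says.** Section 13.3.1 gives one rule for laboratory results in both arms: they "constitute adverse events only if they induce clinical signs or symptoms or require treatment or further diagnostic tests". It sets no grade threshold.

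The calendar in section 7.1 schedules chemistry, including AST, ALT, creatinine and glucose, at the start of every cycle in both arms.

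The explicit instructions for low-grade values sit in guidelines for managing atezolizumab:
- Hepatic, Grade 2 (table in 9.2.2): "Monitor LFTs more frequently until return to baseline values", with corticosteroids if the event lasts more than 5 days.
- Renal, Grade 2 (table in 9.1): specialist referral and corticosteroids.
- Hyperglycemia, Grade 1 or 2 (table in 9.2.4): "Investigate for diabetes. If patient has Type 1 diabetes", with further handling that depends on the result.

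For carboplatin, the transaminase row of 9.3.2.1 reads "Grade 3: Decrease AUC by 1 Grade 4: discontinue". That table has no creatinine or glucose row; its catch-all row also starts at Grade 3.

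For reporting, section 17.4 says: "Adverse medical events will be tabulated. NCI toxicity Grade 3 and Grade 4, and laboratory abnormalities will be listed".

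**The concern.** When a laboratory value becomes an adverse event only because of the response to it, the event rate measures management as well as toxicity. That does no harm to a comparison if management is the same in both arms. Here it is not: below Grade 3 the response is written down for patients on atezolizumab and discretionary for patients on carboplatin alone, and section 8.1 makes the trial open-label. This is differential ascertainment of values that are themselves measured on an equal schedule.

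Section 8.1 names the safety profile among the things the trial evaluates. A reader of the adverse event table would naturally take a higher rate of low-grade hepatic, renal or glucose events on the combination as the added toxicity of atezolizumab. Part or all of such a difference could come from recording. Nothing in 17.4 corrects this, because laboratory abnormalities are to be listed and no summary of grade by arm is specified.

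**Working it through.** The plan states no figure on this point, so there is none to reproduce. The check has two parts.

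**1. The rules side by side, for an asymptomatic value**

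| Value | Patient on atezolizumab | Patient on carboplatin alone |
|---|---|---|
| ALT/AST, Grade 2 | More frequent LFTs; corticosteroids beyond 5 days (9.2.2 table) | No prescribed step in 9.3.2.1; further tests at discretion (7.1, footnote f) |
| Creatinine, Grade 2 | Referral and corticosteroids (9.1 table) | No row in 9.3.2.1; discretion (footnote f) |
| Glucose, Grade 1-2 | Work-up for diabetes (9.2.4 table) | No row in 9.3.2.1; discretion (footnote f) |
| ALT/AST, Grade 3 or higher | Weekly re-testing (footnote f) | Weekly re-testing (footnote f) |

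In the first three rows the prescribed step meets the 13.3.1 condition for the combination arm, while for the control arm the condition is met only if the investigator chooses to act. In the last row it is met in both arms. The asymmetry is thus confined to values below Grade 3.

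Grade 1 hepatic and renal values are left out. There the atezolizumab tables ask only for continued treatment and monitoring, and it is open whether that goes beyond the chemistry that both arms have every cycle.

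**2. An illustration of size**

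Input from the plan: n = 53 per arm (17.2). Assumptions, neither given in the documents:
- q = proportion of patients in each arm with such a value, equal in both arms, 10% to 30%;
- r = fraction of the control-arm values recorded as adverse events, 0 to 1. On the combination all are taken as recorded.

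Expected recorded events: combination 53 × q; control 53 × q × r. Spurious difference: q × (1 − r).

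| q | r = 0 | r = 0.5 | r = 1 |
|---|---|---|---|
| 10% | 5.3 vs 0 (10 points) | 5.3 vs 2.7 (5 points) | 5.3 vs 5.3 (0) |
| 20% | 10.6 vs 0 (20 points) | 10.6 vs 5.3 (10 points) | 10.6 vs 10.6 (0) |
| 30% | 15.9 vs 0 (30 points) | 15.9 vs 8.0 (15 points) | 15.9 vs 15.9 (0) |

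At q = 20% and r = 0.5 this is about 11 versus 5 of 53. As a gauge only, since the plan tests nothing here, two-sided Fisher p-values are 0.17 for 11 versus 5, 0.10 for 16 versus 8, and 0.0005 for 11 versus 0. The result is driven by r as much as by q.

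**The case against.** The strongest reply is that 13.3.1 is one definition for both arms: it asks what a value requires, not which table requires it. Footnote f of the 7.1 calendar allows additional tests in either arm when clinically called for, and requires weekly re-testing at Grade 3 or higher AST/ALT in both. The text of 9.2.2 that says "Imaging of the liver, gall bladder, and biliary tree should be performed to rule out neoplastic or other causes of increased LFTs" names neither arm nor grade, although it stands under atezolizumab hepatitis and leads into the atezolizumab table. If it applies to both arms, the ALT asymmetry shrinks. Section 17.4 also lists laboratory abnormalities separately, so the values are not lost, and it plans no test of event rates between arms.

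Most of this stands, and it limits the point. Recording may differ; it need not. But a prescribed trigger in one arm and a discretionary, unblinded one in the other do not give comparable ascertainment. The creatinine and glucose asymmetry remains whichever way the imaging sentence is read, and a listing is not a comparison by arm.

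Three stronger readings are tempting and not supported:
- *The same value is an event in one arm and never in the other.* That sets r to zero, which footnote f contradicts. The 11 versus 0 contrast is a bound, not an estimate.
- *Dose-limiting myelosuppression escapes the definition in general.* Section 9.3.1 does say that "dose adjustments at the start of a subsequent cycle will be made on the basis of the lowest platelet and neutrophil values" drive carboplatin dosing, and 13.3.1 does not mention dose changes. But 9.3.1 also requires weekly counts whenever chemotherapy is withheld for hematologic toxicity, and 9.3.1.1 allows growth factors for Grade 4 neutropenia; these are further tests and treatment. What remains is a mid-cycle nadir that recovers by Day 1 and is handled by dose reduction alone, and that affects both arms.
- *Section 13.5.6 contradicts 13.3.1 by saying "Grade 4 and 5 events must be reported as serious adverse events".* That is a footnote to a grading scale for events not listed in CTCAE. It is not shown to govern neutrophil counts.

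**Conclusion.** The point holds in a limited form. Adverse event rates for ALT/AST, creatinine and glucose abnormalities below Grade 3 are not comparable between arms, because the combination arm has prescribed triggers for recording them and the control arm has discretionary ones. The direction is towards overstating the added toxicity of atezolizumab.

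The size cannot be fixed from the documents. With half of control values recorded, the spurious difference is 5 to 15 percentage points for prevalences of 10% to 30%; it is zero if control values are worked up as fully as those on the combination. These figures assume equal true prevalence and complete recording on the combination. The harm is a misleading rate difference in a descriptive table, not a false test result. The definition works alike in both arms for Grade 3 or higher AST/ALT. The primary PFS analysis and the sample size are untouched.

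**What to change.** In section 17.4, add a table by randomized arm, restricted to time before crossover, of the worst CTCAE grade for ALT/AST, creatinine and glucose, derived directly from the laboratory results scheduled alike in both arms under the 7.1 calendar. Leave out unscheduled repeat tests, since these are themselves prompted by the arm-specific guidelines. State that between-arm conclusions on these toxicities rest on this table and not on adverse event forms. Because worst grade also rises with time on treatment, show the number of scheduled assessments alongside.

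The definition in 13.3.1 can stay as it is. Adding Grade 3 or higher to it would do nothing for low-grade values, and adding dose holds would bring in another trigger that at Grade 2 is written for atezolizumab only. No clinical instruction needs to change for this purpose.

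The cost is one extra table from values already collected.
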